3.2 Primary Study Endpoints

The primary endpoint for this study is to determine the effects of iron sucrose on 1) self-reported symptoms of autonomic dysfunction assessed by a validated questionnaire and 2) cardiovascular indices measured by tilt table testing.

3.3 Primary Safety Endpoints

Subjects will be continuously monitored during iron sucrose infusion and for no less than thirty minutes following the conclusion of the infusion. During this time, subjects will have continuous cardiopulmonary monitoring of heart rate and oxygen saturation, with blood pressure measurement no less than every fifteen minutes. Subjects will also be clinically assessed by medical staff from the clinical research unit for side effect symptoms. Signs and symptoms of side effects will be recorded in the subject's study record. The primary investigator will review all side effects and correlation to dose amount and infusion rate will be carefully monitored. All serious side effects will be reported promptly to the IRB. Evidence that serious side effects occur at a rate beyond that reported in manufacture labeling will be reported promptly to the IRB and will be potential cause for study termination.

All subjects will have ferritin, iron, and total iron binding capacity measured prior to iron infusion as well as one week following infusion. Evidence of iron overload at the screening visit will preclude subject participation in the study. Evidence of iron overload following the infusion will result in medical management recommendations from the primary investigator. Data will be monitored for evidence of dose-dependent iron overload. If a subject is found to develop clinically significant iron overload, the primary investigator will promptly report to the IRB and this will be potential cause for study termination.

4 Subject Selection Enrollment and Withdrawal

4.1 Inclusion Criteria

• Adolescent patients (age 12 to 21 years) with chronic (>3 months) symptoms of orthostatic intolerance, including but not limited to lightheadedness, syncope, headache, fatigue, weakness, sweating, nausea and heart palpitations.

• Symptomatic orthostatic heart rate increment ≥40 bpm during a 10 minute 70 degree head up tilt study

- Presence of non-anemic iron deficiency, defined as serum ferritin levels <20 ug/L with hemoglobin no less than 1 gm/dL below the normal reference range as defined for age and gender
- Consent obtained from responsible guardian AND from subjects, 12-17 years of age
- Consent obtained for subjects 18 years of age and older

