Diagnosis and Main Inclusion Criteria	Adolescent subjects 12-21 years of age who have a diagnosis of Postural Orthostatic Tachycardia Syndrome and non-anemic iron deficiency as defined by a serum ferritin level of less than or equal to 20 ug/L			
Study Product, Dose, Route, Regimen	5 mg/kg of intravenous iron sucrose supplied as Venofer ® (maximum dose of 200 mg). Iron sucrose will be diluted to 1 mg of elemental iron in 1 mL of NaCl 0.9% (maximum volume of 210 mL).			
Duration of Administration	Single dose administration			
Reference therapy	Normal saline (NaCl 0.9%) 5 mL/kg (maximum volume 210 mL)			

Version5

	Data will be visually inspected for normality. Group comparisons will
	include Fisher's exact test for categorical variables and Wilcoxon rank
Statistical	sums for continuous variables. Confidence intervals will be calculated
Methodology	at 95%. All P-values will be 2-sided with values less than 0.05
	considered significant. All analyses will be performed on an "intention
	to treat" basis.

1 Introduction

This document is a clinical research protocol for a human research study. This study will be carried out in accordance with the applicable United States government regulations and Mayo Clinic research policies and procedures.

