The dose selected for the study intervention is 5 mg/kg of Venofer® (iron sucrose) with a maximum dose of 200 mg. The dose will be diluted in normal saline 0.9% to a final concentration of 1 mg of elemental iron to 1 mL of normal saline 0.9%. In the study from Crary et al., doses up to 7 mg iron/kg up to a maximum dose of 300 mg were found to be safe and effective [20]. Five mild reactions were reported and included one patient with headache, two patients with abdominal pain, one patient with transient mild low blood pressure and one patient with fainting. One 15 year old female had a serious allergic reaction that responded to treatment. This patient was treated with 500 mg of iron sucrose, which was above the recommended maximum dose of 300 mg. In a similar study performed by Pinsk et al., doses of 5 mg iron/kg were used in pediatric patients and also found to be well tolerated with minimal adverse reactions [21].

In a single-dose pharmokinetics study of Venofer, patients with NDD-CDK ages 12 to 16 (N=11) received intravenous bolus doses of Venofer at 7 mg/kg (maximum 200 mg) administered over 5 minutes. Following single dose Venofer, the half-life of total serum iron was 8 hours[28].

•

In this pilot study, subjects will receive only one dose of iron sucrose.

Although adolescents are increasingly responsible for their health care decisions, there is an extensive literature highlighting poor prescription medication adherence in this population [18]. Oral iron supplements, in particular, are commonly discontinued due to patient complaints of gastric irritation and lack of palatability [19]. Nausea is also a common complaint of patients diagnosed with POTS, further complicating oral iron supplementation compliance. Given these limitations, intravenous iron supplementation has been used clinically for correction of iron deficiency in select adolescent patients.

2 Study Objectives

- 1. To assess whether a single infusion of iron sucrose will improve orthostatic symptoms as measured on a validated survey instrument in adolescent subjects with POTS and non-anemic iron deficiency
- 2. To assess whether a single infusion of iron sucrose will improve cardiovascular indices, specifically a reduction in heart rate change during a ten minute head up tilt, in adolescent subjects with POTS and non-anemic iron deficiency.

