4.2 Exclusion Criteria

- Orthostatic hypotension (decrease of systolic BP>30 mmHg and/or diastolic BP>15mmHg within 3 minutes of 70 degree head up tilt study)
- Pregnant or lactating females
- The presence of failure of other organ systems or systemic illness that can affect autonomic function
- Concomitant therapy with anticholinergic, alpha-adrenergic antagonists, betaadrenergic antagonists or other medications which could interfere with autonomic testing. Patients may participate if the potentially interfering medication is held for five half-lives prior to the study
- Laboratory evidence of anemia or iron overload
- Personal history of hematochromatosis or first degree relative with hematochromatosis
- Known sensitivity to Venofer® (iron sucrose injection, USP) or other intravenous iron preparation

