4.3 Subject Recruitment, Enrollment and Screening

Subjects will be recruited for this study from patients seen in the Department of Pediatric and Adolescent Medicine (DPAM) on the Mayo Clinic Rochester campus. The study will be advertised to medical providers within DPAM, particularly those practicing in the divisions of General Pediatrics and Adolescent Medicine (GPAM), Pediatric Neurology, Pediatric Cardiology, Pediatric Gastroenterology and Community Pediatrics and Adolescent Medicine (CPAM). Study information will be shared with these providers through verbal communication, printed materials and e-mail. The information will include inclusion and exclusion criteria, contact information for the Primary Investigator and study coordinator and brief study overview.

Patients will be screened by a study investigator or the study coordinator for review of study entry requirements.

Study enrollment and screening:

- 1. Will take place between 21 days and the day of first study visit
- 2. Will take place either at patient point of care or the Clinical Research Unit
- 3. Will review and document the following:
 - a. Consent and assent forms based on age of subject

- b. Subject demographics
- c. Physical exam by Mayo Clinic medical provider within 12 weeks of study enrollment
- d. Lab data (CBC, ferritin, total serum iron, percent iron saturation) within 12 weeks of study enrollment that meets inclusion and exclusion parameters
- e. Current medication review and compliance with exclusion parameters
- f. Randomization procedure to treatment or placebo group

Patients meeting the criteria will be offered participation in the study. A screening log will be kept to document reasons for ineligibility and for non-participation of eligible candidates. Those choosing to enroll will meet with a research study team member to complete the consent process. A research record will be generated for each study subjects. Documentation that the subject satisfied inclusion and exclusion criteria will be made.

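### Do sections 4.1 and 4.2 conflict over whether a slightly low hemoglobin bars entry?

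*Combined protocol and SAP*

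**What the plan says.** Section 4.1 (Inclusion Criteria) has one line for the iron criterion. It opens "Presence of non-anemic iron deficiency, defined as serum ferritin levels <20 ug/L with hemoglobin" and goes on to set the hemoglobin limit, "hemoglobin no less than 1 gm/dL below the normal reference range as defined for age and gender". The line therefore sets a cut-off and also says what the protocol means by non-anemic iron deficiency.

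Section 4.2 (Exclusion Criteria) lists "Laboratory evidence of anemia or iron overload". It gives no hemoglobin value and does not point back to 4.1.

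Section 4.3 asks for screening laboratory data, including a CBC, "within 12 weeks of study enrollment that meets inclusion and exclusion parameters". The same blood count is thus held against both lists.

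The title and the objectives in section 2 describe the target population as non-anemic; the first objective, for example, concerns effects "in adolescent subjects with POTS and non-anemic iron deficiency". The Study Summary row on diagnosis and main inclusion criteria defines the condition by ferritin alone, as a "serum ferritin level of less than or equal to 20 ug/L", where 4.1 has "serum ferritin levels <20 ug/L".

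**The concern.** A common laboratory meaning of anemia is hemoglobin below the reference range for age and gender. Put that meaning into 4.2 and a subject just under the range satisfies the inclusion line and fails the exclusion line on one blood count. Nothing else in the document defines anemia for eligibility, and 4.3 adds no cut-off.

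Three things could be at stake. Some subjects might be admitted or refused depending on who reads the criteria, since screening may be done by an investigator or by the coordinator. The screening log might give inconsistent reasons for ineligibility. And the published population could be either adolescents with in-range hemoglobin only or a group that includes borderline-low values, which matters in a trial whose title stresses the absence of anemia.

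The differing ferritin signs add to the impression that the entry criteria were not fully checked against one another.

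**Working it through.** The documents state no figure to reproduce, so the check is a comparison of texts.

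**Step 1: the admitted set under each reading.** Let L be the lower reference limit for a subject's age and gender. Section 4.1 is taken to require hemoglobin (Hb) of at least L − 1 g/dL.

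| Hb | 4.1 | 4.2 if anemia means below L | 4.2 if anemia means below the 4.1 limit |
|---|---|---|---|
| at or above L | met | not excluded | not excluded |
| from L − 1 up to L | met | excluded | not excluded |
| below L − 1 | not met | excluded | excluded |

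The readings differ only in the middle row, a band 1 g/dL wide.

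**Step 2: which reading fits the text.** Under the first reading the trial admits Hb at or above L, exactly as if the 1 g/dL allowance had never been written; every subject it lets in is removed again by 4.2. Under the second, the allowance has effect and the lists agree. Section 4.1 uses the form of a definition, and 4.2 uses the opposite term without redefining it. Ordinary construction takes the undefined term as the complement of the defined one.

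**Step 3: how many subjects.** The documents give neither L nor a hemoglobin distribution, so the share in the band cannot be calculated. Each such subject is 1/30 = 3.3% of the planned total, and there may be none.

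**Step 4: effect on the comparison.** Section 4.3 lists the laboratory review ahead of randomization, and section 5.3 leaves the 1:1 assignment to the research pharmacy, so a screener's reading is applied before the arm is assigned. Section 7.2 specifies between-group Wilcoxon and Fisher tests on an intention-to-treat basis. Neither those tests nor the population in 7.3 names a hemoglobin limit. Whichever reading is used, the arms are drawn from the same pool.

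**Step 5: age of the screening sample.** The sample may predate enrollment by 12 weeks, and enrollment itself "Will take place between 21 days and the day of first study visit". The maximum age at infusion is 84 + 21 = 105 days. This concerns how current the value is, not which limit applies to it. A fresh CBC is drawn at Visit 1 in any case.

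**Step 6: ferritin.** The set at or below 20 ug/L and the set below 20 ug/L differ by the single value 20 ug/L.

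**The case for a change.** The best argument for acting is that one of the two lines must be faulty. If 4.1 governs, the anemia exclusion adds nothing; if it does not, 4.2 cancels an allowance that 4.1 expressly grants. The protocol never says which, and an entry criterion ought to give one answer for every hemoglobin value. The question could also reopen after allocation, because the schedule in section 6 places randomization at screening but repeats the eligibility review at Visit 1, where a new CBC is taken. Finally, the background in section 1.1 separates catecholamine findings in iron deficiency with anemia from those without, so anemia status is not a side issue.

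Part of this stands: the cross-reference is missing, and the wording alone does not compel the second reading. The rest carries less weight. Restating an inclusion limit as an exclusion is common and harmless, and the 4.2 line still does separate work on iron overload. Inconsistent screening is possible but would be visible: this is one center, and 4.3 requires both a log of reasons for ineligibility and documentation that the criteria were met. A borderline value found after allocation does not disturb an intention-to-treat analysis. As to the label, non-anemic is defined openly in 4.1, a small margin below the range is a design choice any reader can see, and section 7.2 tabulates baseline clinical variables by group.

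A supportive analysis restricted to in-range subjects has also been suggested. In a trial of 30 it might exclude nobody, and otherwise it would only reduce an already small sample. No gain has been shown for it.

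**Conclusion.** The concern reads the text accurately but identifies a missing cross-reference, not an unavoidable contradiction. The protocol's own definition of non-anemic most naturally supplies the meaning of anemia in 4.2, and following the plan on that footing gives a sound result. The ferritin mismatch is a clerical slip that matters only for a value of exactly 20 ug/L.

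At most, the effect falls on who is enrolled within a 1 g/dL band and on how the population is described; the number involved is unknown and may be zero. The treatment comparison is unaffected. This rests on two assumptions: that the screeners apply one reading throughout, and that the report states the hemoglobin rule actually used. Nothing here says which hemoglobin limit or ferritin sign is clinically right. Bringing the wording of the Study Summary, 4.1 and 4.2 into line would be editorial tidying, and neither the design nor the analysis depends on it.

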4.2 Exclusion Criteria

- Orthostatic hypotension (decrease of systolic BP>30 mmHg and/or diastolic BP>15mmHg within 3 minutes of 70 degree head up tilt study)
- Pregnant or lactating females
- The presence of failure of other organ systems or systemic illness that can affect autonomic function
- Concomitant therapy with anticholinergic, alpha-adrenergic antagonists, betaadrenergic antagonists or other medications which could interfere with autonomic testing. Patients may participate if the potentially interfering medication is held for five half-lives prior to the study
- Laboratory evidence of anemia or iron overload
- Personal history of hematochromatosis or first degree relative with hematochromatosis
- Known sensitivity to Venofer® (iron sucrose injection, USP) or other intravenous iron preparation

4.3 Subject Recruitment, Enrollment and Screening

Subjects will be recruited for this study from patients seen in the Department of Pediatric and Adolescent Medicine (DPAM) on the Mayo Clinic Rochester campus. The study will be advertised to medical providers within DPAM, particularly those practicing in the divisions of General Pediatrics and Adolescent Medicine (GPAM), Pediatric Neurology, Pediatric Cardiology, Pediatric Gastroenterology and Community Pediatrics and Adolescent Medicine (CPAM). Study information will be shared with these providers through verbal communication, printed materials and e-mail. The information will include inclusion and exclusion criteria, contact information for the Primary Investigator and study coordinator and brief study overview.

Patients will be screened by a study investigator or the study coordinator for review of study entry requirements.

Study enrollment and screening:

- 1. Will take place between 21 days and the day of first study visit
- 2. Will take place either at patient point of care or the Clinical Research Unit
- 3. Will review and document the following:
 - a. Consent and assent forms based on age of subject

- b. Subject demographics
- c. Physical exam by Mayo Clinic medical provider within 12 weeks of study enrollment
- d. Lab data (CBC, ferritin, total serum iron, percent iron saturation) within 12 weeks of study enrollment that meets inclusion and exclusion parameters
- e. Current medication review and compliance with exclusion parameters
- f. Randomization procedure to treatment or placebo group

Patients meeting the criteria will be offered participation in the study. A screening log will be kept to document reasons for ineligibility and for non-participation of eligible candidates. Those choosing to enroll will meet with a research study team member to complete the consent process. A research record will be generated for each study subjects. Documentation that the subject satisfied inclusion and exclusion criteria will be made.

For subjects less than 18 years of age, the parent or legal guardian will be required to participate in the consent process along with the subject. The consent form will be reviewed by the study team member. An opportunity will be given for questions. Subjects will be asked to reflect the purpose and interventions of the study back to the research study team member. A waiting period for contemplation will be offered to the potential subjects. Subjects aged 12-17 years old will sign giving assent AND the parent or legal guardian will sign the consent form. Subjects 18 years of age will sign the consent form. All signatures will be witnessed and co-signed by a study team member. The original form will be stored in the subject's research record.

Subjects will be provided with a copy of the consent form and will be provided a copy of subject responsibility during the study.

4.4 Early Withdrawal of Subjects

4.4.1 When and How to Withdraw Subjects

Subjects may stop their participation in the study at any time. Withdrawal of consent or assent will terminate the subject's participation in the study. The Principal Investigator will follow up with subjects to determine if ongoing medical management that may be indicated for patient safety as a result of study discontinuation. If the subject was in the treatment arm of the study, this may include follow up laboratory studies to assess laboratory response to therapy. Medical recommendations will be made by the Principal Investigator based on these results. The Principal Investigator will document reasons for subject dropout in the research record.

If a subject is withdrawn from the study, an additional subject may be enrolled to maintain the statistical power of the study.

In addition, the Principal Investigator or Mayo Clinic may stop the study at any time if there are severe adverse events or if adverse events are reported at a frequency higher than expected.

Subjects may be withdrawn from the study prior to completing all of the study if there is failure to adhere to the subject responsibility parameters.

Subject responsibility during study:

- 1. Subjects will be asked to stop taking medications that can potentially interact with tilt table test results at least 5 half-lives prior to study entry. This includes, but is not limited to anticholinergic, alpha-adrenergic antagonists and beta-adrenergic antagonists
- 2. Subjects will be asked to avoid caffeine and nicotine for at least 24 hours before each study site visit
- 3. Upon enrollment, subjects will be asked to discontinue iron supplements and/or vitamins containing iron until after the second study visit is complete
- 4. Subjects of child-bearing potential must have a negative urine beta-HCG (pregnancy test) prior to study entry
- 5. Subjects who are sexually active and able to become pregnant must agree to use one of the birth control methods listed below until after the last study site visit:
 - a. Hormonal methods, such as birth control pills, patches, injections, vaginal ring or implants
 - b. Barrier methods (such as a condom or diaphragm) used with a spermicide (a foam, cream, or gel that kills sperm)
 - c. Intrauterine device (IUD)
 - d. Abstinence (no sex)

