4.4.2 Data Collection and Follow-up for Withdrawn Subjects

Even though a subject has withdrawn from the study, it may be important to collect some follow-up data on such subjects throughout the protocol defined follow-up period. Such data is important to the integrity of the final study analysis since early withdrawal could be related to the safety profile of the study drug. If a subject withdraws consent to participate in the study, for subject safety reasons, attempts will be made to obtain permission to collect follow up information whenever possible.

5 Study Drug

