5.5 Subject Compliance Monitoring

Subjects will receive only one dose during the study. No additional medication adherence will be required.

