7.1 Sample Size Determination

The two primary outcome variables in this study will be change in score on the COMPASS-31 survey and change in postural heart rate increase. For an anticipated change in the COMPASS-31 survey of 10 points, a sample size of 15 subjects per group (30 total) setting alpha at 0.05 and beta at 0.80 would be an adequate sample size to reject or accept the null hypothesis (power estimate >80%). For an anticipated change in postural tachycardia from 50 beats per minute to 30 beats per minute, a sample size of 15 subjects per group (30 total) setting alpha at 0.05 and beta at 0.80 would be adequate an adequate sample size to reject or accept the null hypothesis (power estimate >80%).

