7.2 Statistical Methods

Descriptive Statistics

Univariate descriptive statistics and frequency distributions will be calculated, as appropriate for all variables. Baseline values for demographic, clinical, and outcome variables (primary and secondary) will be tabulated for the treatment groups. These analyses will help identify potential confounding variables to be used as covariates in sensitivity analyses. Distributions across subgroups used in randomization will be compared to assess whether the randomization was successful in equalizing distributions of these prognostic variables across treatment groups. Putative prognostic variables that will be investigated through these descriptive analyses include subjective symptoms of autonomic dysfunction and cardiovascular indices.

Handling of Missing Data

Continuous data monitoring will be done by both study coordinator and the Primary Investigator using computer based systems. Scheduled review of study documentation by study coordinator and Primary Investigator will take place at a frequency of no less than every four to six weeks to assure that all reports are on file, accurate and complete. Prior to data analysis, trends and outliers will be reviewed to consider for potential missing data.

Primary Hypothesis: Treatment of iron deficiency with intravenous iron sucrose in an adolescent with Postural Orthostatic Tachycardia Syndrome will reduce their score on the COMPASS-31 survey by 10 points.

Data will be visually inspected for normality. Group comparisons will include Fisher's exact test for categorical variables and Wilcoxon rank sums for continuous variables. Confidence intervals will be calculated at 95%. All P-values will be 2-sided with values less than 0.05 considered significant. All analyses will be performed on an "intention to treat" basis

Secondary Hypothesis 1: Treatment of iron deficiency with intravenous iron sucrose in an adolescent with Postural Orthostatic Tachycardia Syndrome will reduce heart rate change during tilt table testing from 50 beats per minute to less than 30 beats per minute.

Data will be visually inspected for normality. Group comparisons will include Fisher's exact test for categorical variables and Wilcoxon rank sums for continuous variables. Confidence intervals will be calculated at 95%. All P-values will be 2-sided with values less than 0.05 considered significant. All analyses will be performed on an "intention to treat" basis

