9.1 Confidentiality

Information about study subjects will be kept confidential and managed according to the requirements of the Health Insurance Portability and Accountability Act of 1996 (HIPAA). Those regulations require a signed subject authorization informing the subject of the following:

- What protected health information (PHI) will be collected from subjects in this study
- Who will have access to that information and why
- Who will use or disclose that information
- The rights of a research subject to revoke their authorization for use of their PHI.

In the event that a subject revokes authorization to collect or use PHI, the investigator, by regulation, retains the ability to use all information collected prior to the revocation of subject authorization. For subjects that have revoked authorization to collect or use PHI, attempts will be made to obtain permission to collect at least vital status (long term survival status that the subject is alive) at the end of their scheduled study period.

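### Section 4.4.1 allows withdrawal for non-adherence after the single infusion, so Visit 2 primary outcomes of randomised, dosed subjects can be lost despite the intention-to-treat statement

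*Combined protocol and SAP*

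**What the plan says.** Section 4.4.1: "Subjects may be withdrawn from the study prior to completing all of the study if there is failure to adhere to the subject responsibility parameters". The rule is permissive and has no cut-off at dosing. The same section allows an extra subject to be enrolled for each one withdrawn, to protect power.

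The responsibility list in section 4.4.1 has five items. Three clearly run past the infusion: caffeine and nicotine before each site visit, iron products until Visit 2 is complete, and contraception until the last site visit. The pregnancy test is an entry requirement. Interfering medicines are also worded for study entry, but the section 6 schedule repeats the medication review and the eligibility check at Visit 2.

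Section 5.2 places the one dose at Visit 1, and section 5.5 adds: "Subjects will receive only one dose during the study. No additional medication adherence will be required".

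For withdrawn subjects, section 4.4.2 says "it may be important to collect some follow-up data on such subjects throughout the protocol defined follow-up period". It also calls such data important to the integrity of the final analysis. It names no outcome and no visit.

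Section 7.2: "All analyses will be performed on an 'intention to treat' basis". Section 7.3 defines one population, the protocol-compliant one.

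**The concern.** After Visit 1 there is no study treatment to discontinue. Removing a subject for non-adherence at that stage only cancels the remaining measurements: the Visit 2 COMPASS-31 and tilt, and possibly the six-month questionnaire. Section 7.1 names change in COMPASS-31 and change in postural heart rate increase as the two primary outcomes, so the loss falls on the main comparison.

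An intention-to-treat analysis needs outcomes from randomised subjects whatever they did after randomisation. A rule that permits removal for post-dose behaviour works against that. If subjects who still feel unwell are more likely to take iron or caffeine, or to restart a held medicine, the missing outcomes would be disproportionately poor ones. Were that to happen mainly on placebo, the placebo arm would look better than it is and a real effect would be diluted. Other patterns of loss would bias differently. A replacement subject restores the number analysed but not the randomised comparison.

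**Working it through.** **The plan's own figure.** Section 7.1 gives "a sample size of 15 subjects per group (30 total) setting alpha at 0.05 and beta at 0.80", which I read as power 0.80. The effect is 10 points and section 7.2 sets a two-sided 0.05 level. No SD is stated, so 15 per arm cannot be reproduced. The largest SD compatible with 80% power under the normal approximation is

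SD = 10 / [(1.960 + 0.842) × √(2/15)] = 9.78 points.

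Section 7.2 specifies the Wilcoxon rank-sum test. In simulation the exact test has about 80% power at SD 9 with 15 per arm, so SD 9 is the assumed value for the power figures below.

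**Mean shift when outcomes are removed.** Assume normal change scores. If k of n subjects are removed in order of a marker that correlates r with change (r = 1 means the k worst outcomes), the mean of those retained shifts by

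r × (sum of the k largest expected normal order statistics of n) / (n − k), in SD units.

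For n = 15 the three largest are 1.736, 1.248 and 0.948.

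- One removed, r = 0.5: 0.5 × 1.736 / 14 = 0.06 SD.
- Three removed, r = 0.5: 0.5 × 3.932 / 12 = 0.16 SD.
- Worst three removed: 3.932 / 12 = 0.33 SD.

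For assumed SDs of 8 to 16 points, 0.06 SD is 0.5 to 1.0 points and 0.33 SD is 2.6 to 5.2 points, against a 10-point target.

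**Power with full replacement.** Assume SD 9, a true 10-point effect, all losses on placebo, and replacements all entering placebo, so that 15 + k are enrolled there and 15 analysed. The shift is then computed with n = 15 + k. The estimated effect is 10 minus the shift times 9. Power is for the exact Wilcoxon test, by simulation.

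| Loss on placebo | Shift (SD) | Estimated effect | Power |
|---|---|---|---|
| none | 0 | 10.0 | about 80% |
| 1 of 16, r = 0.5 | 0.06 | 9.5 | about 76% |
| 3 of 18, r = 0.5 | 0.14 | 8.7 | about 71% |
| worst 3 of 18 | 0.28 | 7.5 | about 64% |

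The shifts here are smaller than those above because k subjects are removed from 15 + k rather than from 15. If the three losses are unrelated to outcome (r = 0), the estimate stays at about 10 points and power at about 80%. The damage under replacement therefore comes from selection and not from the count.

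**Does another section prevent the loss?** Section 4.4.2 expresses an intention, not a commitment, and its one stated action, seeking permission, concerns subjects who withdraw consent. The missing-data paragraph of section 7.2 describes record review and gives no analysis rule. Section 7.3 offers no intention-to-treat set. Nothing downstream recovers the Visit 2 outcomes.

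**The case against.** The rule is discretionary, so a reader who infers that outcomes *are* lost goes too far; the text supports only that they can be. A caffeine or nicotine breach would normally come to light with the subject already at Visit 2, where the assessments could still be done.

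A reader might also infer that treatment response drives the non-adherence. The documents neither say so nor exclude it. The link is plausible for iron, caffeine or a restarted medicine and weak for contraception. For interfering medicines, a continuing duty has to be argued from the Visit 2 recheck, because the item itself is tied to study entry.

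Section 4.4.2 is not purely about safety: it ties data on withdrawn subjects to the integrity of the analysis, over a follow-up period that includes Visit 2. The vital-status wording in section 9.1 ("attempts will be made to obtain permission to collect at least vital status") might be read as the minimum for this rule, but it concerns revoked authorization and sets no minimum for investigator withdrawal.

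Blinding of the investigator limits removal by arm, though not loss related to symptoms. Finally, three losses all on placebo is a stress case, and the plan does not say which arm a replacement enters.

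These points limit the strength and size of the concern. They do not supply a rule that keeps the Visit 2 outcomes.

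**Conclusion.** The concern holds as a gap in the plan: withdrawal for non-adherence stays open after the only dose, and no section secures the primary outcomes of a dosed subject who is withdrawn, although intention to treat is promised. The direction and size of any bias cannot be derived from the documents. The range runs from minor (one loss, about 0.06 SD) to material (worst three of 15, about 0.33 SD), with power between about 76% and 64% in the replaced cases. These figures rest on normal change scores, losses confined to placebo and, for power, an SD of 9 with replacement into the same arm. The documents do not support a claim that the result would be biased against iron by a stated amount. The change is worth making because arms of 15 are sensitive to a few selective losses and the remedy is cheap.

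**What to change.** - **Section 4.4.1:** limit withdrawal from the study for non-adherence to the period before the infusion. After dosing, record the deviation and reschedule within the existing day 7 ±2 window where that resolves it. Otherwise still collect the Visit 2 COMPASS-31 and, if the subject agrees and it is judged safe, the tilt, flagged for sensitivity analysis.
- **Section 4.4.2:** replace the general intention with a commitment to seek the day-7 COMPASS-31 and adverse event information, with the completion date recorded, from every dosed subject who stops site visits and has not refused contact.
- **Section 7.3:** define the intention-to-treat set as all randomised subjects in their assigned arm, and use the protocol-compliant set for sensitivity analysis only.

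The cost is protocol wording and a few extra questionnaires. The downside is that some Visit 2 tilts will be done under imperfect conditions and must be flagged, and some remotely completed questionnaires may fall outside the window, which is why the completion date is needed.
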